8.2. Study Drug Packaging and Labeling

SC setmelanotide and SC placebo will be supplied by Rhythm (manufactured by Recipharm). Oral moxifloxacin and oral placebo will be supplied by the CRU.

Setmelanotide packaging and labeling will be prepared according to the [IMCIVREE \(setmelanotide\) Prescribing Information \(2020\)](#).

To ensure that the subject and site are blinded with respect to subject's randomized treatment assignment, SC placebo and SC setmelanotide are identical in appearance and are supplied in identical packaging. Each package and vial will contain a code that identifies the contents as either SC placebo or SC setmelanotide. For each dose the study pharmacist will select the correct study drug based on the package code and will provide the blinded study medication to the subject for administration.

8.3. Preparation, Handling, and Storage

All study treatments must be stored in a secure, environmentally controlled, and monitored (manual or automated) area in accordance with the labeled storage conditions with access limited to the Investigator and authorized site staff.

SC setmelanotide and SC placebo should be stored at a temperature between 2°C to 8°C. Both SC setmelanotide and SC placebo are stable at room temperature for a short time period.

Oral moxifloxacin and oral placebo should be stored at 25°C, with excursions are permitted to 15-30°C.

8.4. Study Drug Accountability, Handling, and Disposal

Accountability for the study drug at the study site is the responsibility of the Investigator. The Investigator will ensure that the study drug is used only in accordance with this protocol. Where allowed, the Investigator may choose to assign drug accountability responsibilities to a pharmacist or other appropriate individual. Drug accountability records indicating the delivery date to the site, inventory at the site, use by each subject, and return to Rhythm (or disposal of the drug, if approved by Rhythm) will be maintained by the clinical site. Reasons for departure from the expected dispensing regimen must also be recorded. The Sponsor or its designee will review drug accountability at the site during monitoring visits.

All unused study drug supplies and equipment will either be returned to Rhythm or destroyed after the site close-out visit. The Sponsor, or designee, will verify study drug disposition at the site close-out visit. If the study drug is returned to Rhythm, documentation of the shipment will be provided. If the study drug is destroyed by the site, a Certificate of Destruction will be provided to Rhythm, or designee, by the site to document the disposal.

9. PHARMACOKINETIC ASSESSMENTS

Serial blood samples for determination of setmelanotide and moxifloxacin concentrations in plasma will be collected at the timepoints indicated in the SoA ([Table 1](#)). All efforts should be made to collect samples within the sampling windows specified in [Table 1](#); however, collection of samples outside of the window will not be considered protocol deviations. For all PK blood samples, the actual (clock) time that the sample is collected will be recorded in source documents and the eCRF. For timepoints at which vital signs, PK blood samples, and/or ECGs are all to be collected, ECGs should be collected first followed by vital signs then PK samples, with the timing of the PK sample occurring at the nominal time.

Plasma will be harvested from PK samples and will be frozen, shipped to a bioanalytical laboratory designated by the Sponsor. Plasma samples will be analyzed for setmelanotide and moxifloxacin concentrations using validated analytical methods, as detailed in the laboratory manual. Samples collected after placebo dosing will not be analyzed.

10. ASSESSMENT OF SAFETY

10.1. Safety Parameters

Safety and tolerability of setmelanotide will be assessed by monitoring and recording of all AEs throughout the study (setmelanotide and moxifloxacin AEs reported separately). Regular monitoring of 12-lead safety ECGs, C-SSRS, clinical laboratory assessments, vital signs, physical examinations, and concomitant medications will be conducted as detailed in the SoA ([Table 1](#)) and below. Subjects will return to the CRU for a Follow-up visit 7 ± 2 days after receiving the last SC dose to assess for AEs and other safety parameters as described in the SoA ([Table 1](#)).

10.1.1. Demographic, Medical History, and Concomitant Medication Review

Medical history and demographic data including the subject's sex, race, date of birth, and concomitant medication use will be obtained for all subjects during the Screening period ([Table 1](#)).

The medical history should be updated on when the subject enters the CRU on Day -2 (prior to first dose of study drug on Day 1), to assess continued study eligibility and adherence to final inclusion/exclusion criteria. This medical history update includes a review for changes from Screening as well as a review of the subject's recent medication use to assess whether any changes have occurred since the previous visit.

A review of concomitant medications will be conducted during the Screening Period and throughout the study. Any medications taken by study subjects will be reviewed by the Investigator or Sponsor's Medical Monitor to determine whether it is expected to interfere with study procedures or compromise subject safety and will be recorded in source documents and on the appropriate eCRF.

10.1.2. Physical Examination

A complete physical examination will include review of peripheral lymph nodes, head, eyes (including conjunctiva), ears, nose, mouth and oropharynx, neck, heart, lungs, abdomen, musculoskeletal (including back and extremities), and neurologic assessments. All physical examinations are to be conducted in adequate light.

Changes from baseline in any physical examination findings identified by the Investigator as clinically significant must be recorded as an AE on the appropriate eCRF.

10.1.3. Comprehensive Skin Examination

Each subject will receive a complete, comprehensive skin exam as part of Screening, prior to any treatment. If any concerning lesions are identified, the subject will be referred to a dermatologist for assessment and potential biopsy prior to study start. If the pre-treatment biopsy results are of concern, the subject will be excluded from the study.

10.1.4. Fitzpatrick Scale

Each subject is to be categorized for skin type according to the Fitzpatrick scale ([Fitzpatrick 1975](#)). The Fitzpatrick Scale is depicted in Appendix [14.1](#).

10.1.5. Weight and Height

Weight and height will be recorded at the time points designated in the SoA ([Table 1](#)) for the calculation of body mass index (BMI) as follows:

$$BMI \ (kg/m^2) = \frac{weight \ (kg)}{height \ (m)^2}$$

10.1.6. Vital Signs

Vital signs include systolic and diastolic BP, HR, pulse rate, and tympanic (ear) body temperature (°C). BP and HR will be obtained in the supine position following at least 5 minutes of rest in the supine position at each timepoint designated in the SoA ([Table 1](#)). BP and HR will be measured using the same arm for each reading. Repeat measures and more frequent monitoring can be implemented for significant increases in BP or HR.

For timepoints at which vital signs, PK blood samples, and/or ECGs are all to be collected, ECGs should be collected first followed by vital signs then PK samples, with the timing of the PK sample occurring at the nominal time.

10.1.7. 12-Lead Electrocardiogram (ECG)

Continuous Holter 12-lead ECGs (for C-QTc analysis; collected by Holter monitors) and single 12-lead safety ECGs will be obtained at the timepoints detailed in the SoA ([Table 1](#)). The following guidelines will be applied for ECG measurements obtained using a Holter monitor:

- ECG technicians should be thoroughly trained in the administration of a 12-lead ECG, the institution's specific protocols and procedures for ECG tests and the requirements of the study protocol.
- ECG analysts will be blinded to the treatment, timepoint, and subject.
- The same make and model of ECG machine with the same style of leads should be used for all subjects. Such equipment should be recently serviced and calibrated. Machine calibration records and performance data should be maintained on file.
- Subjects should be in a supine position and have rested for 10 minutes before and 5 minutes after each timepoint.
- For Holter ECG extractions, the ECG will be captured for 5 minutes after the subject has been supine for 10 minutes. The subject will remain supine for additional 5 minutes after the end of Holter extraction.

Continuous Holter ECGs will be read with manual adjudication at a central laboratory.

For timepoints at which vital signs, PK blood samples, and/or ECGs are all to be collected, ECGs should be collected first followed by vital signs then PK samples, with the timing of the PK sample to occur at the nominal time.

10.1.8. Columbia Suicide Severity Rating Scale (C-SSRS)

The C-SSRS is a tool used not only to predict suicide attempts but to assess the full range of evidence-based ideation and behavior items, with criteria for next steps (e.g., referral to a mental

health professional [MHP]). Two versions of the C-SSRS will be administered according to the SoA ([Table 1](#)):

1. The baseline/Screening version of the scale combines the Baseline and Screening forms to assess suicidality in a subject's lifetime and during a predefined time. This version can assess a subject's lifetime suicidality for data collection purposes as well as eligibility based on inclusion/exclusion criteria.
2. The Since Last Visit version of the scale assesses suicidality since the subject's last visit. This version is meant to assess subjects who have completed at least one initial C-SSRS assessment and should be used in every subsequent visit. The 'Since Last Visit' version of the C-SSRS is asking about any suicidal thoughts or behaviors the subject/participant may have had since the last time the C-SSRS was administered.

To be eligible for the study, a subject cannot have a suicidal ideation of type 4 or 5 on the C-SSRS at Screening, a history of suicide attempt in the last 20 ears, or any suicidal behavior in the last month.

Any deviation from the intended use of the instrument should be documented by the Investigator, along with the reason for the deviation.

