2. SCHEDULE OF ASSESSMENTS

The Schedule of Assessments (SoA) is presented in [Table 1](#).

Table 1: Schedule of Assessments

Study Period	Screening		Check-In	Baseline	Treatment										Follow-up	Treatment Discontinuation
Study Day Assessment	-28 to -2		-2	-1	1	2-6	7	8	9	10	11-14	15	16	17	23 ± 2	7 ± 4 days after last SC dose
Informed consent	X															
Inclusion/exclusion review	X		X													
Medical history review	X															
Physical exam ^a	X			X											X	X
Comprehensive skin exam ^b	X															
Fitzpatrick classification scale	X															
Height and weight ^c	X			X											X	X
Vital signs ^d	X			X											X	X
Pregnancy test ^e	X			X												X
FSH test	X			X												
Urine drug screen	X			X												
CRU confinement			X	X	X	X	X	X	X	X	X	X	X			
CRU discharge														X		
Fasting ^f			X					X				X				

Study Period	Screening	Check-In	Baseline	Treatment											Follow-up	Treatment Discontinuation
Study Day Assessment	-28 to -2	-2	-1	1	2-6	7	8	9	10	11-14	15	16	17	23 ± 2	7 ± 4 days after last SC dose	
Meal administration ^g			X				X	X	X	X	X	X	X			
Setmelanotide administration ^h				X	X	X	X	X	X	X	X	X	X			
Moxifloxacin administration ⁱ									X				X			
PK sampling ^j									X			X				
Continuous 12-lead ECGs (Holter monitor) ^{k,l}			X							X			X			
Safety 12-lead ECGs ^{l,m}	X		X			X							X	X	X	
Clinical labs ⁿ	X		X			X							X	X	X	
Adverse events	X			Continuous											X	
Concomitant medication review	X			Continuous											X	
C-SSRS ^o	X		X										X		X	
		■								■						

Study Period	Screening		Check-In	Baseline	Treatment												Follow-up	Treatment Discontinuation
Study Day Assessment	-28 to -2		-2	-1	1	2-6	7	8	9	10	11-14	15	16	17		23 ± 2	7 ± 4 days after last SC dose	

CRU = Clinical Research Unit; C-SSRS = Columbia Suicide Severity Rating Scale; ECG = electrocardiogram; FSH = follicle stimulating hormone; INR = international normalized ratio; PK = pharmacokinetic; PT = prothrombin time; PTT (or aPTT) = partial thromboplastin time.

^a A full physical exam will be conducted at Screening. A brief physical exam will be conducted at each check-in, baseline, study discharge, and follow-up.

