^j Blood samples for quantification of setmelanotide and moxifloxacin concentrations will be collected at pre-dose and 0.5, 1, 1.5, 2, 2.5, 3, 4, 5, 6, 7, 8, 9, 10, 12, 16, and 24 hours post-dose on Days 10 and 16. The PK samples collected at 0.5 hours post-dose will have a sampling window of \pm 2 minutes, samples collected from 1 hour though 2.5 hours post-dose will have a sampling window of \pm 5 minutes, samples collected from 3 hours through 10 hours post-dose will have a sampling window of \pm 10 minutes, and samples collected from 12 through 24 hours postdose will have a sampling window of \pm 20 minutes; however, collection of samples outside of the window will not be considered protocol deviations. The timing of all PK samples should be recorded to the nearest minute. For timepoints at which vital signs, PK blood samples, and/or ECGs are all to be collected, ECGs should be collected first followed by vital signs then PK samples, with the timing of the PK sample to occur at the nominal time.

^k Holter ECGs will be extracted at Day -1 and on Days 10 and 16 at the following timepoints: pre-dose and 0.5, 1, 1.5, 2, 2.5, 3, 4, 5, 6, 7, 8, 9, 10, 12, 16, and 24 hours post-dose. The Day -1 extractions will begin at 7:30 AM (the time of anticipated dosing on Days 10 and 16).

^l For ECG collection, subjects will rest in the supine position for at least 10 minutes before and 5 minutes after each timepoint. For timepoints at which vital, PK blood samples, and/or ECGs are all to be collected, ECGs should be collected first followed by vital signs then PK samples, with the timing of the PK sample to occur at the nominal time.

^m Safety ECGs will be collected at the Screening visit, CRU baseline (Day-1), final CRU discharge, and the Follow-up visit.

ⁿ Safety clinical laboratory tests will include: hematology with platelet count and standard indices, chemistry panel (includes sodium, potassium, chloride, CO₂, albumin, total protein, glucose, BUN, creatinine, uric acid, AST, ALT, GGT, CPK, alkaline phosphatase, total bilirubin, direct bilirubin, LDH, calcium, phosphorus, magnesium), and urinalysis with microscopic analysis if positive findings on dipsticks warrant further examination. Safety laboratories will also include a coagulation profile (PT or INR, and PTT also referred to as aPTT).

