^o In order to be eligible for the study, at Screening, a subject cannot have a suicidal ideation of type 4 or 5, a history of a suicide attempt in the past 20 years, or any suicidal behavior in the last month. If at any time during the study a subject has a suicidal ideation of type 4 or 5, or any suicidal behavior, the subject should be referred to a mental health professional.

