10.2.6. Depression or Suicidality

A subject should be referred to an MHP if he/she has:

- Any suicidal behavior.
- Any suicidal ideation of type 4 or 5 on the C-SSRS.

A referral to a MHP should also be made if in the opinion of the Investigator it is necessary for the safety of the subject. If a subject's psychiatric disorder can be adequately treated with psycho- and/or pharmacotherapy, then the subject, at the discretion of the MHP, should be continued in the study.

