6 APPENDICES

6.1 Schedule of Assessments

Table 6-1 Schedule of Assessments

Study Period	Screening		Check-In	Baseline	Treatment										Follow-up	Treatment Discontinuation
Study Day Assessment	-28 to -2		-2	-1	1	2-6	7	8	9	10	11-14	15	16	17	23 ± 2	7 ± 4 days after last SC dose
Informed consent	X															
Inclusion/exclusion review	X		X													
Medical history review	X															
Physical exam ^a	X			X										X	X	X
Comprehensive skin exam ^b	X															
Fitzpatrick classification scale	X															
Height and weight ^c	X			X										X	X	X
Vital signs ^d	X			X										X	X	X
Pregnancy test ^e	X			X										X		X
FSH test	X			X												
Urine drug screen	X			X												
CRU confinement			X	X	X	X	X	X	X	X	X	X	X			
CRU discharge														X		
Fasting ^f			X					X				X				
Meal administration ^g				X				X	X	X	X	X	X			

Study Period	Screening		Check-In	Baseline	Treatment										Follow-up	Treatment Discontinuation
Study Day Assessment	-28 to -2		-2	-1	1	2-6	7	8	9	10	11-14	15	16	17	23 ± 2	7 ± 4 days after last SC dose
Setmelanotide administration ^h					X	X	X	X	X	X	X	X	X			
Moxifloxacin administration ⁱ										X			X			
PK sampling ^j										X			X			
Continuous 12-lead ECGs (Holter monitor) ^{k,l}				X						X			X			
Safety 12-lead ECGs ^{l,m}	X				X		X						X	X	X	
Clinical labs ⁿ	X				X		X						X	X	X	
Adverse events	X		←		Continuous				→							X
Concomitant medication review	X		←		Continuous				→							X
C-SSRS ^o	X				X									X		X

CRU = Clinical Research Unit; C-SSRS = Columbia Suicide Severity Rating Scale; ECG = electrocardiogram; FSH = follicle stimulating hormone; INR = international normalized ratio; PK = pharmacokinetic; PT = prothrombin time; PTT (or aPTT) = partial thromboplastin time

^a A full physical exam will be conducted at Screening. A brief physical exam will be conducted at each check-in, study discharge, and follow-up.

^b A comprehensive skin evaluation will be performed by the Investigator at Screening. If any concerning lesions are identified during the screening period, the subject should be referred to a dermatologist for assessment and potential biopsy and results should be confirmed as to whether the lesion is benign prior to first dose of setmelanotide. If the pre-treatment biopsy results are of concern, the subject will be excluded from the study.

^c Height will only be collected at Screening.

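### Neither schedule marks the C-SSRS at the Day 23 ± 2 Follow-up, so completers have no structured suicidality screen in the 4 to 8 days after discharge (minor, cheap improvement)

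*Protocol*

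**What the plan says.** Protocol 10.1.8 sets the timing by reference: "Two versions of the C-SSRS will be administered according to the SoA". It then describes the Since Last Visit version as "meant to assess subjects who have completed at least one initial C-SSRS assessment and should be used in every subsequent visit". The recall period of that version runs "since the last time the C-SSRS was administered".

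In Protocol Table 1 the C-SSRS row is marked at Screening, Day -1, Day 17 and Treatment Discontinuation, and Follow-up is empty. The C-SSRS row of SAP Table 6-1 ends the same way: marked at Day 17, blank at Day 23 ± 2, marked in the last column, headed "7 ± 4 days after last SC dose".

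Other safety assessments are done at Follow-up. Footnote m reads "Safety ECGs will be collected at the Screening visit, CRU baseline (Day-1), final CRU discharge, and the Follow-up visit", and footnote a reads "A brief physical exam will be conducted at each check-in, baseline, study discharge, and follow-up". Clinical laboratory tests are marked there too.

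On referral to a mental health professional, Protocol 10.2.6 lists any suicidal behavior, the item "Any suicidal ideation of type 4 or 5 on the C-SSRS", and investigator opinion. Footnote o to the C-SSRS row, the same in both documents, states when referral applies: "If at any time during the study a subject has a suicidal ideation of type 4 or 5, or any suicidal behavior". Under Protocol 5.5 a subject completes the study only after the Follow-up visit.

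**The concern.** Completers leave the unit on Day 17 and are next seen at Follow-up. The referral rule is still in force over that interval, but no scheduled instrument measures the ideation ground. What remains is adverse event collection through Follow-up (Protocol 10.2.4 and 10.2.5), which relies on non-leading questions, spontaneous reports, observation and examination, together with referral for behavior or on the investigator's judgment. None of these asks directly about ideation.

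The schedule also treats similar times after dosing differently. A subject who stops early gets a C-SSRS about a week after the last dose. A subject who completes the titration is seen about a week after the last dose and does not get one. Any C-SSRS data from beyond the day after the last dose would therefore come almost entirely from early leavers.

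What is at stake is a small subject-safety gain and a clear instruction to the site. The trial's QTc conclusions are not involved.

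**Working it through.** **1. Is the Follow-up cell really blank?** Some rows of both tables are displaced in the text version, so the C-SSRS row was compared with neighbouring rows in the same block of Protocol Table 1. That block has 15 visit columns; column 13 is Day 17, column 14 is Follow-up and column 15 is Treatment Discontinuation.

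| Row | Marked columns | Day 17 | Day 23 ± 2 | Discontinuation |
|---|---|---|---|---|
| Protocol, safety ECG | 1, 3, 6, 13, 14, 15 | X | X | X |
| Protocol, clinical labs | 1, 3, 6, 13, 14, 15 | X | X | X |
| Protocol, C-SSRS | 1, 3, 13, 15 | X | blank | X |
| SAP Table 6-1, C-SSRS (last three columns) | – | X | blank | X |

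The safety ECG row includes all four visits named in footnote m, Follow-up among them, so the alignment holds at that end of the table. It also shows a Day 7 mark that footnote m does not list. In the SAP the safety ECG row is displaced and cannot serve as a control, and the C-SSRS baseline mark falls under Day 1. The last three C-SSRS cells in the SAP still agree with the protocol.

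**2. Visit days.** The last SC dose is on Day 16 and Follow-up is 7 ± 2 days later: 16 + 7 = 23, so Day 21 to Day 25. This reproduces the plan's Day 23 ± 2.

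**3. Length of the gap.** Days without a scheduled C-SSRS = Follow-up day − 17. Days from first dose (Day 1) to Follow-up = Follow-up day − 1.

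| Follow-up | Gap (days) | First dose to Follow-up (days) | Share |
|---|---|---|---|
| Day 21 | 21 − 17 = 4 | 21 − 1 = 20 | 4/20 = 20.0% |
| Day 23 | 23 − 17 = 6 | 23 − 1 = 22 | 6/22 = 27.3% |
| Day 25 | 25 − 17 = 8 | 25 − 1 = 24 | 8/24 = 33.3% |

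**4. What the Day 17 form covers.** The previous C-SSRS is on Day -1, so the Day 17 recall period takes in the 17 − 1 = 16 days from first dose to Day 17, which is the whole dosing period. The uncovered days all follow the last dose.

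**5. Completers against early leavers.** The Follow-up visit falls 7 − 2 = 5 to 7 + 2 = 9 days after the last dose, without a C-SSRS. The Treatment Discontinuation visit falls 7 − 4 = 3 to 7 + 4 = 11 days after the last dose, with one. The first window lies inside the second.

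**6. Size of the change.** 60 planned completers × 1 form = 60 forms.

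**The case against.** The strongest reply is that the schedule is deliberate and no rule is broken. Section 10.1.8 hands timing to the Schedule of Assessments, and the sentence about later visits can be read as saying only which form to use once a first one has been given. The marks fit a plan of one exit form per subject: at discharge for completers and at the discontinuation visit for early leavers. In SAP Table 6-1 the pregnancy test row ends with the same pattern. Footnote o does not tie referral to a form being due, and no C-SSRS is scheduled between Day 1 and Day 16 either. Adverse events are collected through an in-person Follow-up, the subjects are healthy volunteers with significant psychiatric history excluded, and the documents show no sign of a post-treatment hazard.

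Much of this stands. The blank may be intended, this is not a contradiction, and few events are expected. The percentages in the working measure calendar time and not risk. Exclusion criterion 9 bars any lifetime suicide attempt, whereas footnote o and 10.1.8 give a 20-year limit; that discrepancy does not change the point.

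Two things are left. The absence of forms during Days 1 to 16 is made good by the Day 17 look-back, but nothing makes good the absence after Day 17. And the exit-form reading does not explain why the question is worth asking about a week after dosing for one set of subjects and not for the other.

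**Conclusion.** The concern holds, as a minor and inexpensive improvement. Completers have no scheduled C-SSRS for 4 to 8 days before their last study contact (6 days, 27% of the time from first dose, at the nominal visit). During that time the referral rule applies, but its ideation ground is not measured by any planned assessment.

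C-SSRS coverage of the dosing period, the C-SSRS change-from-baseline endpoint, the QTc analyses, assay sensitivity and sample size are all unaffected. The conclusion rests on the Follow-up cell being blank as read, which the two tables support jointly, and on dosing ending on Day 16 as planned.

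**What to change.** Mark the Since Last Visit C-SSRS at the Day 23 ± 2 Follow-up in Protocol Table 1 and in SAP Table 6-1. No analysis text needs to change: SAP 4.12.1 already summarizes the scale by time of collection, and Protocol 11.3.4 already covers change from baseline to any value after dosing.

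The cost is one mark in each table, about 60 short questionnaires (a few minutes each) at an existing visit, and one more time point in the C-SSRS summary. If the sponsor does not intend a C-SSRS at Follow-up, 10.1.8 should say that the later form is used only at visits where the schedule calls for it. That would settle the wording but leave the gap.
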